7.1 DEMOGRAPHIC AND OTHER BASELINE CHARACTERISTICS

Only descriptive statistics are planned for this section of the report, based on the TS.

The data will be summarised by treatment group and in total.

7.2 CONCOMITANT DISEASES AND MEDICATION

Frequency tables are planned for this section of the report, based on the TS.

Concomitant diseases will be coded using the latest version of the coding system of the Medical Dictionary for Drug Regulatory Activities (MedDRA). Medications will be coded using the latest version of the World Health Organization Drug Dictionary (WHO-DD). The coding version number will be displayed as a footnote in the respective output.

The diagnoses and medications will be listed. Subjects without any concomitant diagnoses or concomitant therapies should be marked with a "No" in the respective column.

The relevance of the concomitant therapies to the evaluation of PK will be decided no later than at the RPM.

7.3 TREATMENT COMPLIANCE

Section 4.3 of the CTP: *Compliance will be assured by administration of all trial medication in the study centre under supervision of the investigating physician or a designee. The measured plasma concentrations will provide additional confirmation of compliance.*

It is not intended to list the compliance separately. Any deviations from complete intake will be addressed in the RPM and described in the CTR.

7.4 PRIMARY ENDPOINTS

Refer to TSAP [Section 7.8](#) for a description of the analysis of safety and tolerability of BI 1358894.

7.5 SECONDARY ENDPOINTS

7.5.1 Key secondary endpoints

This section is not applicable as no key secondary endpoints have been specified in the CTP.

7.5.2 Secondary endpoints

7.7 EXTENT OF EXPOSURE

Descriptive statistics are planned for this section of the report based on the TS. The date and time of drug administration will be listed for each subject.

7.8 SAFETY ANALYSIS

All safety analyses will be performed on the TS.

If not stated otherwise, the safety results will be sorted by treatment group.

The safety data for treated subjects who failed to complete the study (dropouts or withdrawals) will be reported as far as their data are available. All withdrawals will be documented and the reason for withdrawal recorded.

7.8.1 Adverse events

AEs will be coded with the most recent version of MedDRA.

The analyses of AEs will be descriptive in nature and will be based on BI standards.

The standard AE analyses will be based on the number of subjects with AEs (and not on the number of AEs).

For analysis, multiple AE occurrence data on the electronic case report form (eCRF) will be collapsed into an AE provided that all of the following applies:

- All AE attributes are identical (lower level term (LLT), intensity, action taken, therapy required, seriousness, reason for seriousness, relationship, outcome, AE of special interest (AESI))
- The occurrences were time-overlapping or time-adjacent (time-adjacency of two occurrences is given if the second occurrence started within one hour after end of the first occurrence).

Section 5.2.6.1.5 of the CTP: *The AESI for this trial is hepatic injury, as defined by the following alterations of hepatic laboratory parameters:*

- *An elevation of AST (aspartate aminotransferase) and/or ALT (alanine aminotransferase) ≥ 3 -fold ULN combined with an elevation of total bilirubin ≥ 2 -fold ULN measured in the same blood sample, or*
- *Aminotransferase (ALT, and/or AST) elevations ≥ 10 -fold ULN*

These lab findings constitute a hepatic injury alert and the subjects showing these lab abnormalities need to be followed up according to the 'DILI checklist' provided in the ISF. In case of clinical symptoms of hepatic injury (icterus, unexplained encephalopathy, unexplained coagulopathy, right upper quadrant abdominal pain, etc.) without lab results (ALT, AST, total bilirubin) available, the Investigator should make sure that these parameters are analysed, if necessary in an unscheduled blood test. Should the results meet the criteria of hepatic injury alert, the procedures described in the DILI checklist should be followed.

The analysis of adverse events will be based on the concept of treatment emergent AEs.

Section 1.2.6 of the CTP: *The residual effect period (REP) for BI 1358894, the time interval when measureable drug levels or pharmacodynamics (PD) effects are still likely to be present after the last administration, is not known at this early stage of development.*

Section 7.3.4 of the CTP: *Therefore, measurements planned or AEs recorded prior to intake of trial medication will be assigned to the screening period, those between trial medication intake until the trial termination date will be assigned to the treatment period.*

For more details see the TSAP ADS plan.

According to ICH E3 ([7](#)), AEs classified as ‘other significant’ needs to be reported and will include those non-serious and non-significant adverse events with

- (i) ‘action taken = discontinuation’ or ‘action taken = reduced’, or
- (ii) marked haematological and other lab abnormalities or lead to significant concomitant therapy as identified by the investigator or Clinical Trial Leader at the RPM.

An overall summary of AEs (including AESIs) will be presented.

The frequency of subjects with AEs will be summarized by treatment, primary system organ class (SOC) and preferred term (PT). Separate tables will be provided for subjects with other significant AEs according to ICH E3 ([7](#)), for subjects with serious AEs, for subjects with drug-related AEs, for subjects with drug related serious adverse events and for subjects with AESIs.

The SOC and PTs will be sorted by frequency (within SOC). The MedDRA version number will be displayed as a footnote in the respective output.

In addition, frequencies of subjects with non-serious AEs that had an incidence of > 5% for at least one treatment will be summarised by treatment, primary SOC and PT.

7.8.2 Laboratory data

The analyses of laboratory data will be descriptive in nature and will be based on BI standards.

Laboratory data will be analysed qualitatively via comparison of laboratory data to their reference ranges. Values outside the reference range as well as values defined as possible clinically significant will be flagged in the data listings.

Clinically relevant findings in laboratory data will be reported as baseline conditions (at screening) or as AEs (during the trial) if judged clinically relevant by the investigator, and will be analysed as such.

It is the investigator's responsibility to decide whether a lab value is clinically significant abnormal or not (at the RPM at the latest).

Descriptive statistics of laboratory data will be calculated by planned time point based on the worst value of the subject at that planned time point (or assigned to that planned time point).

The mean normalised values and SD over time for all laboratory parameters, except for parameters that are measured at a single time point will be displayed graphically. The time span is from baseline to post examination.

7.8.3 Vital signs

Descriptive statistics over time including change from baseline will be performed for vital signs (blood pressure and pulse rate), as well as respiratory rate (RR) and orthostatic tests. In the listing the difference from baseline will also be displayed.

Descriptive statistics will be calculated by planned time point based on the last value of the subject at that planned time point (or assigned to that planned time point).

Clinically relevant findings in vital signs will be reported as AEs.

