#### **5.2.2 Vital signs**

Systolic and diastolic BP as well as PR will be measured by a blood pressure device at the times indicated in the [Flow Chart](#), after subjects have rested for at least 5 min in a supine position. All recordings should be made using the same type of blood pressure recording instrument on the same arm if possible. Respiratory rate (RR) will be measured after 5 minutes of rest in supine position for at least 1 minute.

Orthostatic tests will be performed at the time points indicated in the Flow Chart. Subjects should have spent at least 5 min in the supine position before blood pressure and pulse rate are measured the first time. A further 2 measurements will be performed immediately after standing up and after 3 min in a standing position. The term “Orthostatic dysregulation” will be used to describe adverse events that occur during orthostatic testing. Orthostatic hypotension is defined as a reduction in systolic BP of  $\geq 20$  mm Hg or in diastolic BP of  $\geq 10$  mm Hg within 3 minutes of standing and will be recorded as an AE. Orthostatic hypotension may be accompanied by symptoms of dizziness, diaphoresis, a decline in blood pressure, tachycardia (PR  $> 100$  bpm), or even fainting (which is reflected in the assessment of AE intensity).

At the time points given in the Flow Chart, the following sequence of measurements should be adhered to: 12 lead-ECG and vital signs will be done before blood sampling; orthostatic testing will be done after blood sampling. While standing up, subjects will be accompanied by staff.

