## **5.2.4      Electrocardiogram**

### **5.2.4.1    12-lead resting ECG**

Twelve-lead resting ECGs (I, II, III, aVR, aVL, aVF, V1 - V6) will be recorded using a computerised electrocardiograph (MAC 2000 ECG machines, GE Healthcare) at the time points given in the [Flow Chart](#).

In order to achieve a stable heart rate at rest and to assure high quality recordings at comparable resting phases, all ECGs will be recorded for a 10-second duration after the subjects have rested for at least 5 minutes in a supine position. The site personnel will be instructed to assure a relaxed and quiet environment so that all subjects are at complete rest during the recordings. ECG assessment will always precede all other study procedures of the same time point (except blood drawing from an intravenous cannula which is already in place) to avoid impact of sampling on the ECG quality.

Electrode placement will be performed according to the method of Wilson, Goldberger and Einthoven modified by Mason and Likar (hips and shoulders instead of ankles and wrists). Precise electrode placement will be marked with an indelible mark on the skin to allow reproducible placement throughout the study.

Triple ECGs will be recorded (within 180 sec) at all-time points on Day 1 to Day 3 (48 h) for Dose Groups 1 and 2 or on Day 1 to Day 7 (144h) for Dose Group 3. At all remaining time points, single ECGs will be recorded.

All locally printed ECGs will be evaluated by the investigator or a designee.

ECGs may be repeated for quality reasons (like alternating current artefacts, muscle movements, electrode dislocation). For time points with triple ECGs, all three single ECGs will be repeated. For the repeats due to quality reasons, only the repeated ECG recordings will be sent to the central ECG lab, whereas the initially recorded ECGs will be discarded.

Additional (unscheduled) ECGs may be collected by the investigator for safety reasons. These ECGs are assigned to the prior scheduled time point. Unscheduled ECGs will not be included into the statistical analysis of interval lengths.

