treatment, system organ class and preferred term. SAEs, AESIs (see Section [5.2.6.1](#)) and other significant AEs (according to ICH E3) will be listed separately.

Previous and concomitant therapies will be presented per treatment group without consideration of time intervals and treatment periods. Laboratory data will be compared to their reference ranges. Values outside the reference range as well as possibly clinically significant values will be highlighted in the listings. Additionally, differences from baseline will be evaluated.

Vital signs or other safety-relevant data will be assessed with regard to possible on-treatment changes from baseline.

The ECG variables QT, HR, QTcF, QTcB, PR, QRS, and RR obtained from the centralised evaluation of 12-lead ECG recordings will be the basis for the derivation of quantitative and categorical ECG endpoints. These endpoints and their analyses will be described in the TSAP.

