6.7 BASELINE, TIME WINDOWS AND CALCULATED VISITS

The baseline value is defined as the last measurement before administration of BI 1358894 or Placebo.

Section 6.1 of the CTP: *Exact times of measurements outside the permitted time windows will be documented. The acceptable time windows for screening and the end of trial examination are provided in the CTP Flow Chart.*

Study measurements and assessments scheduled to occur ‘before’ trial medication administration on Day 1 are to be performed and completed within a 2 h-period prior to the trial drug administration except PK sample. A blank sample for PK will be collected within 3 h before drug administration.

The acceptable deviation from the scheduled time for vital signs, orthostatic testing and ECG will be ± 10 min and laboratory tests will be ± 30 min for the first 4 h after trial drug administration and ± 30 min thereafter.

[...]

Adherence to time windows will be checked via the consistency check listings at the RPM.

Unscheduled measurements of laboratory data or vital signs will be assumed to be repeat measurements of the most recent scheduled measurement (e.g. for follow-up or confirmation of a particular value). Therefore, unscheduled measurements will be assigned to the planned time point of the previous scheduled measurement.

There will be a centralised evaluation of the 12-lead ECG recordings at the time points and for the ECG recordings specified in the [Table 6.7: 1](#) below:

Section 5.2.4.1 of the CTP: *Triple ECGs will be recorded (within 180 sec) at all-time points on Day 1 to Day 3 (48 h) for Dose Groups 1 and 2 or on Day 1 to Day 7 (144h) for Dose Group 3. At all remaining time points, single ECGs will be recorded.*

Table 6.7: 1 Time schedule of 12-lead ECG recordings

Visit	Day	Planned time [hh:mm] (relative to drug administration)	Study phase	Central evaluation
1	-28 to -1		Screening	NA
2	1	-01:00	Baseline	all 3 single ECGs of the triplicate
		00:30		first of three replicate ECG
		01:00		first of three replicate ECG
		01:30		first of three replicate ECG
		02:00		first of three replicate ECG
		03:00		first of three replicate ECG
		04:00		first of three replicate ECG
		05:00		first of three replicate ECG
		06:00		first of three replicate ECG
		08:00	On treatment	first of three replicate ECG
		12:00		first of three replicate ECG
	2	16:00		first of three replicate ECG
		24:00		first of three replicate ECG
		34:00		first of three replicate ECG
	3	48:00		first of three replicate ECG

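### Vital-sign tables use the last value at each planned time, so an unscheduled recheck overwrites the scheduled reading and can understate transient supine blood-pressure falls

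*SAP*

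**What the plan says.** Two SAP rules have to be read together.

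- **Assignment (SAP 6.7).** Unscheduled vital signs and laboratory values "will be assumed to be repeat measurements of the most recent scheduled measurement", and so "unscheduled measurements will be assigned to the planned time point of the previous scheduled measurement". The SAP gives following up or confirming a particular value as an example of why they are taken.
- **Selection (SAP 7.8.3).** "Descriptive statistics will be calculated by planned time point based on the last value of the subject at that planned time point". The sentence goes on to include values that were only assigned to that time.

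Other safety data in the same trial are handled differently.

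- **Laboratory (SAP 7.8.2).** The assignment rule is the same, but the statistics are "based on the worst value of the subject at that planned time point".
- **ECG (Protocol 5.2.4.1).** "Unscheduled ECGs will not be included into the statistical analysis of interval lengths". A repeat takes the place of the first recording only when it is made for quality reasons: "only the repeated ECG recordings will be sent to the central ECG lab, whereas the initially recorded ECGs will be discarded".

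The stated purpose is in Protocol 7.3.4: "Vital signs or other safety-relevant data will be assessed with regard to possible on-treatment changes from baseline". Protocol 4.2.1 names hypotension and tachycardia as findings from the toxicology studies.

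**The concern.** The SAP itself expects some rechecks to be prompted by the value just seen. If the value that prompted the recheck is then dropped, the data are selected on the outcome. Regression to the mean alone moves the tabulated figure towards normal. If a short-lived fall has already recovered, the figure moves further. The distortion grows with the number of low readings, so it would be larger on an active dose that lowers blood pressure than on placebo. That narrows the descriptive comparison the table is meant to support.

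The minimum is affected as well as the mean, and in a phase I trial with six active subjects per dose a reader looks there first. Orthostatic hypotension has its own safeguard: it is defined by a threshold "within 3 minutes of standing and will be recorded as an AE". A supine fall has none and becomes an adverse event only if the investigator judges it clinically relevant. A transient supine fall not judged relevant and then rechecked would appear in the individual listing but in no summary that the available SAP text describes.

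The replacing value can also be later than its label. From the vital-sign times in the Flow Chart, the lag is under 1 h for time points up to 5 h. It can reach 2 h after the 6 h point and 14 h after the 34 h point, and the gaps are longer still at later visits. These are upper limits. A confirmatory recheck would usually come sooner.

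**Working it through.** The plan states no figure on this point, so there is nothing to reproduce. The mechanism follows from the two rules above. Only its size needs arithmetic, and that arithmetic rests on assumptions.

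**From the documents:** six active subjects per dose group (SAP 6.1); table statistics N, mean, SD, minimum, median and maximum (SAP 7).

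**Assumed:** systolic change X on active ~ N(-10, 10) mmHg; a recheck whenever X ≤ -20 and at no other time; recheck from the same distribution, with correlation r to the first reading.

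**Mean on active**

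- P(X ≤ -20) = Φ(-1) = 0.1587, and E[X | X ≤ -20] = -25.25.
- E[last value] = -10 + 0.1587 × (1 - r) × 15.25.
- r = 0: -7.58. r = 0.5: -8.79. r = 0.8: -9.52.
- If pressure has returned to baseline by the recheck, N(0, 10): -10 + 0.1587 × 25.25 = -5.99.

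**Mean on placebo**, X ~ N(0, 10)

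- P = 0.0228, and E[X | X ≤ -20] = -23.73.
- Shift = 0.0228 × (1 - r) × 23.73 = 0.54, 0.27 and 0.11 for r = 0, 0.5 and 0.8.
- The shifts on active are 2.42, 1.21 and 0.48, so the active-placebo difference shrinks at every r.

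**Other triggers** (r = 0.5): at 15 mmHg the active mean is -8.24, and at 25 mmHg it is -9.35.

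**Expected minimum of six active subjects** (simulation, 400,000 groups)

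| Value tabulated | Expected minimum (mmHg) |
|---|---|
| Scheduled reading | -22.7 |
| Last value, r = 0 | -17.4 |
| Last value, r = 0.5 | -19.7 |
| Last value, r = 0.8 | -21.4 |
| Last value, recovered | -15.8 |

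**Fewer rechecks.** The shift in the mean scales with the share of falls rechecked.

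- 50% rechecked, r = 0.8: -10 + 0.5 × 0.48 = -9.76; expected minimum -22.1.
- 25% rechecked, r = 0.5: -10 + 0.25 × 1.21 = -9.70; expected minimum -22.0.

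**A different set-up.** This simulation takes a within-subject SD of 6 to 10 mmHg, a between-subject SD half as large, a true mean of -10 and the same 20 mmHg trigger. The tabulated mean is -9.3 to -7.6 if the effect persists at recheck and -8.6 to -5.7 if it has resolved. The share of tabulated values at or below -20 drops from 6.8–18.6% to 0.9–5.0% or 0.0–1.2% respectively.

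**One subject in a group of six.** A scheduled -30 rechecked at -5 moves the mean up by (30 - 5)/6 = 4.2 mmHg. In the other direction, a symptom-driven -25 after a scheduled -5 moves it down by (25 - 5)/6 = 3.3 mmHg.

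**The case against.** The rule is stated openly and is coherent. If a repeat is taken to confirm or correct a reading, using the last value follows naturally. The documents describe no on-treatment recheck trigger or frequency, so a recheck after every large fall is an extreme assumption, and readings prompted by new symptoms push the table the other way. The early schedule is dense (0:30, 1:00, 1:30, 2:00 and 3:00, then hourly to 6:00), so a fall that lasts to the next planned time is tabulated there unless it is rechecked again. Differences between data types are not errors in themselves. No hypothesis is tested, and individual values are listed with their difference from baseline. Parts of the SAP and the protocol's further safety endpoints are not in the public text, so another blood-pressure summary may exist.

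Much of this stands. It limits the size and shows that the documents do not fix the net direction. It does not remove the mechanism. The SAP's example explains why an unscheduled value is attached to the previous time point, but not why it should displace a valid scheduled reading. That the bias can run either way, depending on why a recheck was taken, is a further reason not to let rechecks decide what is tabulated. The dense schedule protects against missing lasting falls, not the transient ones at issue here.

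**Conclusion.** The concern holds as a minor point about the choice of analysis. It is not a contradiction in the plan. Under the SAP as written, a recheck replaces a valid scheduled reading in the vital-sign tables, and where rechecks follow low readings those tables understate transient supine falls. On the illustrative assumptions, a mean change of -10 mmHg would be shown as about -6.0 to -9.8, and the expected minimum of six as about -15.8 to -22.1 instead of -22.7. These ranges depend on the assumed trigger, recheck rate, correlation and SD, none of which the documents give.

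The effect is confined to these tables. Adverse events, listings, the sustained-fall escalation rule, the primary endpoint and heart rate from the central ECG reading do not depend on them. The analysis dataset plan cited by the SAP was not available and may add selection detail.

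**What to change.** In SAP 7.8.3:

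1. Base post-dose summaries by planned time on the scheduled measurement. Let a repeat replace it only where the scheduled reading is documented as technically faulty, in line with the ECG quality repeats. Where no such reason is recorded, the scheduled reading stands.
2. Keep the last pre-dose value as baseline, as SAP 6.7 defines it.
3. Add, by treatment, a summary of each subject's lowest supine systolic and diastolic pressure and highest supine pulse rate on treatment, including unscheduled values.

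The cost is a change of wording, a revised selection flag in the analysis dataset and one small table. No additional data have to be collected. The drawback is that an artefact nobody documented may stay in a time-point mean, with its recheck visible in the listing.

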7.8.4 ECG

Continuous safety ECG monitoring (by investigator)

Clinically relevant abnormal findings will be reported as AEs.

No separate listing or analysis of continuous ECG monitoring will be prepared.

12-lead ECG

Abnormal findings, irrespective of whether they originate from central or local evaluation, will be reported as baseline conditions (at screening) or as AEs (during the trial) if judged clinically relevant by the investigator.

All evaluations of ECG data will be based on the TS, except the exposure-response analyses, which are based on the ECGPCS.

Listing of individual data

For all quantitative endpoints, listings of individual data will be shown in Appendix 16.2. For QTcB and RR only listings will be provided. Occurrences of notable findings will be flagged.

Comments regarding the ECGs will be listed.

Categorical endpoints

For the categorical endpoints, frequency tables will be provided.

For all subjects with any notable finding in ECG intervals, a separate listing will be created as end-of-text display (based on the same display template as in Appendix 16.2), and the corresponding time profiles will be shown.

Quantitative endpoints

Descriptive statistics (N, mean, SD, min, median, max) will be provided for the changes from baseline over time of QTcF, HR, QT, PR and QRS. The time profiles of mean and SD for the changes from baseline on treatment will be displayed graphically by treatment.

For QTcF and HR changes from baseline, the relationship to the corresponding plasma concentrations will be evaluated using a random coefficient model. For subjects in the ECGPCS, all time points with available ECG endpoints and valid time-matched drug plasma concentrations will be included. For the handling of missing values, see [Section 6.6](#).

The response variable will be the change from baseline in QTcF (Δ QTcF). The placebo subjects will be included in the analysis, setting their plasma concentrations to zero.

As a first step, it is investigated if there is a potential delayed or accelerated (e.g. due to metabolites) effect of the drug on QTcF. A general visual impression will be provided by overlaying time profiles of plasma concentrations and QTcF changes from baseline (Δ QTcF). These figures will be generated for each subject (presented in Statistical Appendix of the CTR), as well as for means per active treatment (presented in the End-of-Text part of the CTR).

The relationship between BI 1358894 plasma concentrations and QTcF changes from baseline will be investigated in an exploratory manner using a random coefficient model to estimate the difference in means between BI 1358894 and placebo of QTcF change from baseline and its 90% confidence interval at the geometric mean of C_{max} for each dose.

Additionally, the estimated overall slope with its 90% confidence interval will be provided. The used random coefficient model is based on a white paper from Garnett et al. ([8](#)) with Δ QTcF as response variable, centered baseline QTc and plasma concentration as continuous covariates, treatment and time as fixed categorical effects, and a random intercept and slope for each subject. For more details refer to [Section 9.3](#).

For visualization, a scatterplot of the BI 1358894 plasma concentration against the following individual QTcF values will be provided: For each subject on active treatment and each time point, subtract the mean value of all individual observed Δ QTcF values from the placebo group for this time point from the individual observed Δ QTcF value for this subject and time point. This results in estimates for “individual $\Delta\Delta$ QTcF” values, which should only be used for plotting purposes. The corresponding regression line and its pointwise confidence bands as well as and the geometric mean of C_{max} for each dose will additionally be displayed in the plot.

To check model assumptions, the conditional residuals will be plotted and presented in the Statistical Appendix of the CTR. In case of non-linearity or if there is evidence for a delayed effect, further models will be explored in order to better characterise the PK-ECG relationship (e.g. effect compartment models, non-linear models, etc.).

All of the above described graphical and statistical analyses will be also performed for HR in place of QTcF.

Appropriateness of heart rate correction methods of QT interval

To evaluate the appropriateness of the heart rate correction methods, the slope of the relationship of QTcF interval versus RR interval (values log-transformed using the natural logarithm) will be estimated by applying the random coefficient model described in [Section 9.1](#) using all time points. A scatterplot of QTcF vs RR including the overall regression line will be included in the Statistical Appendix of the CTR. The resulting (fixed effect) slope together with two-sided 95% confidence intervals will be included in the footnote for this plot.

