#### **4.1.4 Drug assignment and administration of doses for each subject**

The treatments to be evaluated are outlined in Table 4.1.4: 1 below. The number of units for placebo corresponds to the number of units of the corresponding dose level.

Table 4.1.4: 1 BI 1358894 and placebo treatments, oral administration

Dose	Substance	Pharmaceutical form	Unit strength	Number of units per administration	Total dose
1	BI 1358894	Film-coated tablet	25mg	2 tablet	50 mg
2	BI 1358894	Film-coated tablet	100 mg	1 tablets	100 mg
3	BI 1358894	Film-coated tablet	100 mg	2 tablet	200 mg
1-3	Placebo*	Film-coated tablet	--	identical to active treatment	--

\* Subjects receiving placebo are equally distributed across dose groups

The trial medication will be administered to the subjects, while in a sitting position, as an oral dose together with about 240 mL of water under supervision of the investigating physician or an authorised designee in the morning of Day 1. For drug administration, the so-called four-eye principle (two-person rule) should be applied.

After an overnight fast of at least 10 hours, a high-fat, high-calorie breakfast will be served 30 min before drug administration. The subjects must completely consume the meal prior to drug intake. The composition of the standard high-fat, high-calorie meal is detailed in Table [4.1.4: 2](#); this meal is in compliance with the Food and Drug Administration (FDA) guidance 'Food-Effect Bioavailability and Fed Bioequivalence Studies' [[R03-2269](#)]. For restrictions with regard to diet, see Section [4.2.2.2](#).

Proprietary confidential information © 2019 Boehringer Ingelheim International GmbH or one or more of its affiliated companies

Table 4.1.4: 2

Composition of the high-fat, high-calorie meal

Ingredients	kcal
102g roll	322
105g sausage	337
36g process cheese	122
50g boiled egg (whole content)	76
12g tomato ketchup	14
6g mayonnaise	40
150 mL water	0
Sum 	911

 The total caloric content was supplied approximately as following: 150 kcal as protein, 250 kcal as carbohydrate, and 500 to 600 kcal as fat.

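### The first-step check for a delayed effect on QTcF and HR is drawn without placebo correction, so meal and time-of-day changes can mimic or hide a delay

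*SAP*

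**What the plan says.** SAP 7.8.4 (ECG, quantitative endpoints) sets out the order of work: "As a first step, it is investigated if there is a potential delayed or accelerated (e.g. due to metabolites) effect of the drug on QTcF". The tool is a plot: "A general visual impression will be provided by overlaying time profiles of plasma concentrations and QTcF changes from baseline". It is made for each subject "as well as for means per active treatment". Placebo is not named in these overlays, and the variable is change from baseline only.

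The consequence comes later in the same section: "In case of non-linearity or if there is evidence for a delayed effect, further models will be explored", with effect compartment and non-linear models as examples. No criterion for evidence of delay is given. All these steps are repeated for HR.

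Elsewhere in 7.8.4 the non-drug time course is controlled. The random coefficient model includes placebo subjects at concentration zero and has "treatment and time as fixed categorical effects, and a random intercept and slope for each subject". For the concentration scatterplot, the SAP tells the analyst to "subtract the mean value of all individual observed" ΔQTcF values of the placebo group at the same time point. The resulting values are ones "which should only be used for plotting purposes".

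The ECG baseline is the mean of the pre-dose triplicate, planned at -1:00 (SAP 6.7, Table 6.7: 1). Protocol 4.1.4 states that "a high-fat, high-calorie breakfast will be served 30 min before drug administration". In the protocol Flow Chart, lunch follows the 4 h procedures, dinner is at 10 h, and the 16 h ECG falls at about 01:00.

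**The concern.** ΔQTcF and ΔHR are measured against one morning baseline, planned before a 911 kcal meal. Any change due to meals or clock time adds to the drug effect in the overlay. A non-drug rise in the evening or at night looks like an effect that lags behind concentration. A non-drug rise near the concentration peak can mask a real lag.

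The delay check is thus the one step of the exposure-response work without placebo control. The scatterplot cannot stand in for it, because it plots against concentration and does not show time. At stake is whether an exploratory delay model is added when it is not needed, or left out when it is. A missed true delay would leave a direct-effect model that does not fit and that understates the peak effect at Cmax.

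**Working it through.** The documents state no figure for this check, so there is none to reproduce. The calculations below are illustrative and cover QTcF only.

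**Inputs from the documents.** ECG times 0.5 to 48 h; breakfast at -0.5 h, lunch at 4 h, dinner at 10 h; 01:00 at 16 h; triplicate baseline and one evaluated ECG per later time point; 6 active subjects per dose; 2 placebo per group, so 3 × 2 = 6 pooled.

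**Assumed inputs.** A drug effect E of 5 or 10 ms at peak with no delay; concentration peak at about 3 h or 5-6 h; SD 6 ms; Day 2 lunch and dinner at 28 and 34 h; a non-drug pattern S(t) of amplitude A. S(t) is a 24 h cosine of height A/2 with its peak at 01:00, plus a dip of depth A/2 after each meal, minus the cosine's value at 08:00.

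**Step 1: without noise.** The expected ΔQTcF(t) = E × c(t)/c(peak) + S(t), with c(t) proportional to exp(-0.05t) - exp(-0.9t). On the ECG grid this peaks at 3 h.

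- c(3) = 0.8607 - 0.0672 = 0.7935; c(16) = 0.4493; ratio 0.566.
- For A = 6 ms, S(3) = -3.0 and S(16) = +3.7.
- E = 5: at 3 h, 5.0 - 3.0 = 2.0 ms; at 16 h, 2.8 + 3.7 = 6.5 ms.
- E = 10: at 3 h, 10.0 - 3.0 = 7.0 ms; at 16 h, 5.7 + 3.7 = 9.4 ms.

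The highest uncorrected value is at 16 h although the effect has no delay. Subtracting the expected placebo profile removes S(t), leaving 5.0 against 2.8 ms (or 10.0 against 5.7 ms) and the peak back at 3 h.

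**Step 2: with noise, no true delay.** The ranges run over the assumed scenarios. The AIC columns use the 200 mg mean profile and the 3 h concentration curve.

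| A (ms) | Mean peak ≥ 4 h late, raw | Corrected | Effect compartment preferred by AIC, raw | Corrected |
|---|---|---|---|---|
| 0 | 9-20% | 14-24% | 10-11% | 12-16% |
| 3 | 29-56% | 14-25% | 30-46% | 13-17% |
| 6 | 65-86% | 15-24% | 62-81% | 14-17% |
| 10 | 95-99% | 14-24% | 93-100% | 10-17% |

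A second set (SD 7 ms, half-life 8 or 24 h, night-time peak) gave late peaks in 13-55% raw against 7-31% corrected at 3 ms, and 37-81% against 7-31% at 6 ms.

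**Step 3: the planned model.** A fixed-effect least-squares version with time and treatment factors and placebo included was fitted 400 times per scenario. A true slope of 5 gave means of 4.95-5.20, and a true slope of 10 gave 9.82-10.23. With an SD of about 3 between runs, the simulation error of each mean is 3/√400 = 0.15, so the largest deviation (0.23) is about 1.5 times that error. There is no sign of bias from the time pattern.

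**Step 4: the reverse error.** With a true effect-compartment half-life of 6 h and an assumed afternoon-peaking pattern of 6 ms, a late peak was visible in 18-70% of runs raw against 52-85% corrected. The effect at the time of peak concentration was then 50-54% of its maximum.

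**Step 5: cost of correction.** The SE of a corrected mean is s × √(1/6 + 1/m), with m placebo subjects. At an assumed s = 7 ms:

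- raw: 7/√6 = 2.9 ms;
- m = 6 (up to 48 h): 7 × √(1/3) = 4.0 ms;
- m = 2 (72-144 h, where SAP Table 6.7: 1 has central evaluation for Dose Group 3 only): 7 × √(2/3) = 5.7 ms.

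Extending the SD 7 ms simulation to 144 h with two placebo subjects after 48 h raised the corrected rate of false delay to 10-43%. With no pattern, the raw rate was 3-30%. Raw remained worse at 6 ms and mostly at 3 ms.

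**The case against.** A reader might infer that the overlay decides whether the direct-effect model is kept, and that the reported slope and ΔΔQTcF at Cmax then rest on a model chosen from a confounded picture. The documents do not support this. SAP 7.8.4 plans the random coefficient model and its 90% intervals unconditionally. Further models are explored to describe the relationship better, and nothing says that they replace it. The analysis is exploratory, and Protocol 7.2 plans no hypothesis test.

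Other planned displays can expose a non-drug pattern: mean ΔQTcF profiles by treatment, which include placebo, and conditional residual plots. This stands. What remains is that the SAP does not tie them to the delay check. It also refers to Section 9.3 for model details; that section is not in the public text, so whether it guides model choice is unknown.

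The rates are open to challenge. The pattern, effect size, kinetics and SD are assumed, and the 4 h peak rule is not in the SAP, which relies on visual review of whole profiles. PK sampling to 192 h (Dose Groups 1 and 2) and 672 h (Dose Group 3) may point to a longer half-life than 8-24 h. At an assumed 72-120 h, corrected false delay was 43-64%, so correction alone does not make the check reliable. This also stands.

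Posture is a weak argument for HR, because ECGs follow at least 5 minutes supine (Protocol 5.2.4.1), with the ECG first and meals last at each time point (Protocol 6.1).

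**Conclusion.** The point holds as a weakness in an exploratory diagnostic. The delay check for QTcF and HR lacks the placebo control that the SAP applies in its model and scatterplot, and the trial's own schedule gives non-drug changes a route into the display. The realistic harm is an unnecessary delay model, or a missed one. The planned slope and the estimate at Cmax are not biased by time of day, although a true delay that goes unnoticed would leave the direct-effect model misspecified.

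The direction is firmer than the size. If the non-drug pattern is about 3-6 ms, an apparent delay is mostly more likely without correction. If there is no pattern, correction costs a little. The percentages show sensitivity to assumptions and are not expected rates for this trial. No HR figures were simulated. This is a cheap improvement, not a flaw that undermines the planned estimate.

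**What to change.** In SAP 7.8.4, for the mean overlays, plot active mean minus pooled-placebo mean ΔQTcF at the same planned time, or add the pooled-placebo mean curve to the same figure. Show confidence intervals and the number of placebo subjects at each time point. Do the same for ΔHR. Keep the raw overlays, including the subject-level ones: subtracting one placebo mean from every subject would repeat the same chance pattern across all those figures.

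The cost is a sentence or two in the SAP and a changed input to existing figure programs, with no new data. The downside is added placebo noise, from six subjects up to 48 h and only two at 72-144 h. Late corrected points should therefore be read cautiously and beside the raw profile.
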